Once enrolled through written informed consent, research participants will be assigned to either "standard therapy" or to "standard therapy with IOPI" treatment group by a clinical investigator. This assignment will be in an alternating fashion based on date of enrollment. IOPI treatment consists of 10 repetitions of the IOPI exercises, three times a day on three days per week for 8 weeks. It will take 30 minutes to train the subject on how to do the exercises and record them and that it takes 5-10 minutes to complete 30 repetitions of the exercise. Subjects will be completing a diary related to their exercise regimen.

Subjects will undergo a standard of care modified barium swallow study by clinical staff prior to the onset of therapy to obtain baseline measurements of airway protection and oropharyngeal kinematic function. They will also be asked to complete a Visual Analog Scale (VAS) to rate their dysphagia prior to initiation of therapy, therapy by marking an "X" on a 100mm line indicating their perception of the severity of their dysphagia (0 = least severe, 100 = most severe). They will also be asked to complete a dietary assessment tool/questionnaire consisting of 10 items (EAT-10). Tongue isometric pressure generation (strength) will be measured with the IOPI. This requires the subject to press a small plastic air-filled bulb between the tongue and hard palate, which transfers isometric pressure on the IOPI. The Functional Oral Intake Scale (FOIS) will be used by the clinician to rate current level of oral intake. Finally subjects will be weighed.

Approximately 8 weeks after the initiation of therapy ("standard" or "standard w/ IOPI") individuals will be asked to complete the VAS and the EAT-10, and the clinician will repeat the FOIS and weigh the subjects, once again at their 8-week standard of care clinical follow up visit. 8 weeks is the usual standard of care follow up visit. A modified barium swallow (MBS) test will also be performed as part of standard of care at about the 8 week time point (after therapy). Finally isometric pressure (tongue strength) will be measured at this point.

At 8 weeks, individuals who were assigned to the "standard therapy only" group, who still require swallowing therapy, will be asked if they would like to add the IOPI to their therapy

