3.11 **Identify each of the disease or condition specific subgroups (include healthy volunteers, if applicable) that will be studied.**

Click on the "Add" button and specify for each subgroup:

- 1) how many subjects will undergo research related procedures at this site; and**
- 2) if applicable, how many subjects will be required to undergo screening procedures (e.g., blood work, EKG, x-rays, etc.) to establish eligibility. Do Not include subjects who**

will undergo preliminary telephone screening.

*

Subgroup	Number to undergo research procedures	Number to undergo screening procedures
View Standard Therapy plus IOPI	50	0
View Standard Therapy	50	0

3.12 Provide a statistical justification for the total number of subjects to be enrolled into this research study at the multicenter sites or this site.

* Described below:

This is a pilot study. Enrollment numbers were determined through a review of the referral base and realistic expectations for recruitment.

View: 3.13 - 3.15(a)

Section 3.0 - Human Subjects

3.13 Inclusion Criteria: List the specific criteria for inclusion of potential subjects.

Age 18 and older.

Diagnosed with oral, oropharyngeal, hypopharyngeal or laryngeal cancer having non-surgical treatment with chemoradiation, or radiation therapy alone, resulting in treatment associated dysphagia.

3.14 Exclusion Criteria: List the specific criteria for exclusion of potential subjects from participation.

1. Unable to adhere to assigned therapy program due to cognitive deficits.
2. Surgical treatment for head and neck cancer.
3. unable to give informed consent
4. Past or current history of temperomandibular joint dysfunction
5. Past or current history of myofacial pain disorders

3.15 Will HIV serostatus be evaluated specifically for the purpose of participation in this research study?

* No

If Yes, provide a justification:

View: 4.01 - Version 2

Section 4 - Subject Recruitment and Informed Consent Procedures**4.1 Select all recruitment methods to be used to identify potential subjects:**

Other Strategies: Described below

Advertisements

Upload the advertisements for review:

Name Modified Date

Honest Broker

Identify the name of the honest broker system and name of the specific individuals who will provide those services:

Specify the IRB-assigned honest broker system number (e.g., HB123456):

Upload the signed honest broker assurance agreement:

Name Modified Date

There are no items to display

Recruitment Letters and Scripts

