It will be necessary to collect personal identifiable information as subjects will be followed over a several month time period depending on their clinical treatment. Medical record information will be accessed during participation so personal identifiable information will need to be captured.

Muscle soreness will be managed by decreasing the target pressure of the IOPI device for the subject. This device must be kept out of the reach of children. While the instructions of the device state that a "medical professional should hold onto tube...", all subjects will be instructed on the safe/appropriate method of using the device. This may include a family member assisting in the use of the device or the subject holding on to the tube on their own. This process will be discussed in depth during the instruction period prior to the start of IOPI therapy. Any participant with poor comprehension of these instructions (in the opinion of a research team member) may be removed from the study for safety reasons.

Subjects will be instructed to skip any questions that they are not comfortable answering.

5.2 What steps will be taken in the event that a clinically significant, unexpected disease or condition is identified during the conduct of the study?

* **Addressed below:**

Participants will be under the clinical care of a member of the Department of Otolaryngology. Any disease or condition identified during the course of this research will be addressed following standard clinical procedure.

5.3 All the risk questions (screening, intervention/interaction, follow-up) have been merged into one question (5.1).

View: 5.04

Section 5 - Potential Risks and Benefits of Study Participation

5.4 Do any of the research procedures pose a physical or clinically significant psychological risk to women who are or may be pregnant or to a fetus?

* No

5.4.1 List the research procedures that pose a risk to pregnant women or fetuses:

5.4.2 Describe the steps that will be taken to rule out pregnancy prior to exposing women of child-bearing potential to the research procedures that pose a risk to pregnant women or fetuses:

5.4.3 Describe the measures to prevent pregnancy, and their required duration of use, that will be discussed with women of child-bearing potential during and following exposure to research procedures:

View: 5.05

Section 5 - Potential Risks and Benefits of Study Participation

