5.5.1 List the research procedures that pose a potential risk of genetic mutations/birth

defects:

5.5.2 **Describe the measures to prevent pregnancy, and their required duration of use, in female subjects and female partners of male subjects during and following exposure to research procedures:**

View: 5.06 - 5.06(a)

Section 5 - Potential Risks and Benefits of Study Participation

5.6 **Are there any alternative procedures or courses of treatment which may be of benefit to the subject if they choose not to participate in this study?**

* Yes - Describe below:

If Yes, describe in detail:

Yes. Standard swallowing therapy for individuals with treatment associated dysphagia.

View: 5.07 - 5.07(a)

Section 5 - Potential Risks and Benefits of Study Participation

5.7 **Describe the specific endpoints (e.g., adverse reactions/events, failure to demonstrate effectiveness, disease progression) or other circumstances (e.g., subject's failure to follow study procedures) that will result in discontinuing a subject's participation?**

* Describe below:

It may be possible that subjects may be removed for the following reason:

If subject is unable to cognitively understand the exercises.

Information related to "non-compliance" is important to be noted. Subjects who are non-compliant will not be removed.

View: 5.08 -5.08(a)

Section 5 - Potential Risks and Benefits of Study Participation

5.8 **Will any individuals other than the investigators/research staff involved in the conduct of this research study and authorized representatives of the University Research**

Conduct and Compliance Office (RCCO) be permitted access to research data/documents (including medical record information) associated with the conduct of this research study?

* Yes

5.8.1 Identify the 'external' persons or entity who may have access to research data/documents and the purpose of this access:

Although we do not currently plan on sharing data, should we decide to share data in the future, we will contact the Office of Research to determine whether an agreement needs to be executed.

5.8.2 Will these 'external' persons or entity have access to identifiable research data/documents?

*

No; the research data/documents will be coded and subject identifiers removed prior to access by the external persons

If Yes, describe how they will protect the confidentiality of the research data:

5.9 Has or will a Federal Certificate of Confidentiality be obtained for this research study?

* No

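### Section 5.1.1 allows removal from the study, after arm assignment, for poor comprehension of the IOPI instructions; before week 8 this falls mainly on the IOPI arm and could bias the week-8 comparison

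*Combined protocol and SAP*

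**What the plan says.** Section 5.1.1 describes how patients will be taught to handle the IOPI and then sets a removal rule, given as a safety measure: "Any participant with poor comprehension of these instructions (in the opinion of a research team member) may be removed from the study". On timing it says "This process will be discussed in depth during the instruction period prior to the start of IOPI therapy". It also says that "all subjects will be instructed on the safe/appropriate method of using the device".

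Section 5.7, on ending a subject's participation, gives one reason: "If subject is unable to cognitively understand the exercises". It names no arm. It then says "Subjects who are non-compliant will not be removed".

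The surrounding design is as follows.

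- **Order of events (2.6).** Patients consent, are enrolled, and are then assigned alternately to standard therapy or standard therapy plus IOPI. Exercise training takes 30 minutes. Standard-arm patients are trained for IOPI therapy only at week 8, if they still need therapy and agree to add it.
- **IOPI as a measuring device (2.6).** Tongue strength is measured with the IOPI at baseline and week 8, with no restriction by arm.
- **Eligibility (3.14, item 1).** The protocol excludes patients who are "Unable to adhere to assigned therapy program due to cognitive deficits".
- **Analysis (2.18).** Between-group t-tests are planned at the start and end of the 8 weeks. No analysis set and no missing-data rule are given. Nothing says whether removed patients are assessed at week 8.

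**The concern.** The rule in 5.1.1 acts after the arms have been formed. It rests on one team member's opinion, and no masking is described. It ends study participation, not only use of the device. If it is applied mostly in one arm, the two groups compared at week 8 are no longer the two groups that were assigned.

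Poor comprehension may go with poorer adherence and slower functional recovery. If so, taking such patients out of the IOPI arm while their counterparts stay in the standard arm makes IOPI look better with no true effect. The protocol already accepts the opposite principle for non-compliance, where patients are kept. As it stands, a patient who does not do the exercises stays in the comparison, while one who cannot follow the device instructions may be lost from it.

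**Working it through.** **Step 1: to whom does each removal ground apply before week 8?**

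| Ground | IOPI arm | Standard arm |
|---|---|---|
| 5.1.1: poor comprehension of IOPI handling instructions | Yes, in the instruction period before IOPI therapy | On the natural reading no; therapy training comes only at crossover |
| 5.7: cannot understand the exercises | Yes | Yes, since standard therapy also consists of exercises |
| Non-compliance (5.7) | Not a ground | Not a ground |

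The IOPI arm faces two grounds and the standard arm one.

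**Step 2: inputs for the size.** The arm sizes come from the table in 3.11: 50 + 50 = 100, which agrees with 3.10. Section 3.12 sets the number by feasibility and gives no alpha, power, effect size or SD, so there is no sample-size calculation to reproduce. The following are assumptions:

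- two-sided alpha of 0.05;
- *p*, the share of each arm that comprehends poorly and, in the IOPI arm, is removed;
- *D*, how much worse their outcomes are than everyone else's, in SD.

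**Step 3: bias.** Suppose there is no true effect and removal happens in the IOPI arm only. Set the mean of good comprehenders to 0. The standard arm then averages −*pD*, and the remaining IOPI arm averages 0. The expected difference is *pD* in favour of IOPI.

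**Step 4: error rate.** With 50 per arm the standard error is √(1/50 + 1/50) = 0.20 SD. The bias divided by 0.20 is the shift of the test statistic, and the rejection probability follows from the noncentral t distribution.

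| *p* | *D* | Bias *pD* (SD) | Shift | Two-sided error |
|---|---|---|---|---|
| 5% | 0.5 | 0.025 | 0.125 | 5.2% |
| 10% | 0.5 | 0.05 | 0.25 | 5.7% |
| 5% | 1.0 | 0.05 | 0.25 | 5.7% |
| 10% | 1.0 | 0.10 | 0.50 | 7.9% |

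Reducing the IOPI arm to 50(1 − *p*) and using the normal approximation changes little: the last row becomes 7.8%.

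**Step 5: sensitivity.**

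- *Some removal in the standard arm too.* If half of its poor comprehenders are removed under 5.7, their share among those remaining is (*p*/2)/(1 − *p*/2). For *p* = 10% this is 0.05/0.95 = 0.0526. With *D* = 0.5 the bias is 0.026 SD instead of 0.05.
- *No link with outcome.* *D* = 0 gives no bias.
- *Opposite link.* *D* = −0.5 with *p* = 10% gives −0.05 SD, against IOPI.
- *Wider range.* *p* = 2% with *D* = 0.5 gives 0.01 SD and an error of 5.0%. *p* = 20% with *D* = 1.0 gives 0.20 SD and, by the normal approximation with the reduced arm, 15.6%.

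**The case against.** A reader might infer that removal for poor comprehension can happen only in the IOPI arm, and that the week-8 result must therefore favour IOPI. The documents do not support either step.

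First, 5.7 has no arm limit, so comprehension-based removal as such is not confined to IOPI patients. Section 5.1.1 also speaks of instructing all subjects, and the IOPI measures tongue strength in both arms, which leaves open a reading in which standard-arm patients are instructed too. I think that reading less likely. The text concerns who holds the tube, including help from a family member, and is tied to the start of IOPI therapy. It fits repeated exercise better than a single measurement. But it cannot be excluded.

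Second, the direction depends on prognosis. No section says that poor comprehenders swallow worse at week 8. The rule is also discretionary.

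Third, 3.14 already excludes patients who cannot adhere because of cognitive deficits, and those unable to consent. That shrinks the pool, and the assumed 5% to 10% has no source in the protocol. It does not empty the pool: item 1 refers to the programme already assigned, and comprehension can be poor for other reasons.

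Fourth, this is a pilot sized on feasibility, with many outcomes and no stated primary. At the lower end of the range an error of 5.2% is practically nominal.

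What stands is that the removal is subjective, follows assignment, and has an additional ground in one arm, with no follow-up or as-assigned analysis to protect the comparison.

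**Conclusion.** The concern holds as a risk of bias, not as a demonstrated one. A stated rule permits differential removal after assignment, so this is more than a missing detail. Its effect on the week-8 comparison is probably towards IOPI, provided that poor comprehenders do worse.

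The likely size is small: 0.025 to 0.10 SD, with an error of about 5.2% to 7.9% against an assumed 5%. This rests on three assumptions: 5% to 10% removed, outcomes 0.5 to 1 SD worse, and removal in the IOPI arm only. Relaxing the third shrinks the bias. If comprehension is unrelated to outcome there is none. The change is worth making because the week-8 contrast is the only between-arm comparison planned after treatment, and the remedy costs little.

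**What to change.** Reconcile 5.1.1 and 5.7 so that stopping use of the device on the team's safety judgement does not end study participation. The safety judgement itself stays as it is. For patients who stop, state that they:

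- keep the week-8 MBS, FOIS, weight, VAS and EAT-10;
- have tongue strength measured with the IOPI only if the team judges that safe;
- are analysed in the arm to which they were assigned.

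Report device stops and removals by arm. Apply the existing cognitive exclusion (3.14, item 1) to every patient before the arm is allocated.

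The cost is a few sentences of protocol text. MBS, FOIS and weight are routine care according to 2.7; VAS and EAT-10 are research-only, so these patients complete two short questionnaires. The IOPI effect estimate will be slightly diluted by patients who did not use the device. Some values will be missing for tongue strength, the first outcome listed in 2.17.

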5.5.1 List the research procedures that pose a potential risk of genetic mutations/birth

defects:

5.5.2 **Describe the measures to prevent pregnancy, and their required duration of use, in female subjects and female partners of male subjects during and following exposure to research procedures:**

View: 5.06 - 5.06(a)

Section 5 - Potential Risks and Benefits of Study Participation

5.6 **Are there any alternative procedures or courses of treatment which may be of benefit to the subject if they choose not to participate in this study?**

* Yes - Describe below:

If Yes, describe in detail:

Yes. Standard swallowing therapy for individuals with treatment associated dysphagia.

View: 5.07 - 5.07(a)

Section 5 - Potential Risks and Benefits of Study Participation

5.7 **Describe the specific endpoints (e.g., adverse reactions/events, failure to demonstrate effectiveness, disease progression) or other circumstances (e.g., subject's failure to follow study procedures) that will result in discontinuing a subject's participation?**

* Describe below:

It may be possible that subjects may be removed for the following reason:

If subject is unable to cognitively understand the exercises.

Information related to "non-compliance" is important to be noted. Subjects who are non-compliant will not be removed.

View: 5.08 -5.08(a)

Section 5 - Potential Risks and Benefits of Study Participation

5.8 **Will any individuals other than the investigators/research staff involved in the conduct of this research study and authorized representatives of the University Research**

Conduct and Compliance Office (RCCO) be permitted access to research data/documents (including medical record information) associated with the conduct of this research study?

* Yes

5.8.1 Identify the 'external' persons or entity who may have access to research data/documents and the purpose of this access:

Although we do not currently plan on sharing data, should we decide to share data in the future, we will contact the Office of Research to determine whether an agreement needs to be executed.

5.8.2 Will these 'external' persons or entity have access to identifiable research data/documents?

*

No; the research data/documents will be coded and subject identifiers removed prior to access by the external persons

If Yes, describe how they will protect the confidentiality of the research data:

5.9 Has or will a Federal Certificate of Confidentiality be obtained for this research study?

* No

5.10 Question has been moved to 5.17

5.11 Question has been moved to 5.16

View: 5.12 - 5.13

Section 5 - Potential Risks and Benefits of Study Participation

5.12 Does participation in this research study offer the potential for direct benefit to the research subjects?

Yes - Describe the direct benefit that subjects may receive as a result of study participation. Indicate if all, or only certain, of the subjects may derive this potential benefit.

Describe the benefit:

It is possible that individuals assigned to the group using IOPI may experience an accelerated

rate of recovery related to their dysphagia. They may also experience an enhanced recovery.

5.13 Describe the data and safety monitoring plan associated with this study. If the research study involves multiple sites, the plan must address both a local and central review process.

The investigators and research staff will meet at least monthly to discuss the progress of the research study and to review all information related to this research study including recruitment, confidentiality, adverse events and patient safety. The Principal Investigator, [name], will oversee these meetings. A summary report will be provided to the IRB as part of the renewal process.

View: 5.14 - 5.17

Section 5 - Potential Risks and Benefits of Study Participation

5.14 What precautions will be used to ensure subject privacy is respected? (e.g. the research intervention will be conducted in a private room; the collection of sensitive information about subjects is limited to the amount necessary to achieve the aims of the research, so that no unneeded sensitive information is being collected, drapes or other barriers will be used for subjects who are required to disrobe)

All conversations with the patients will be conducted in closed door rooms as part of their regular clinical appointment. Information collected will be the minimum necessary to contribute to the specific aims of this project.

5.15 What precautions will be used to maintain the confidentiality of identifiable information? (e.g., paper-based records will be kept in a secure location and only be accessible to personnel involved in the study, computer-based files will only be made available to personnel involved in the study through the use of access privileges and passwords, prior to access to any study-related information, personnel will be required to sign statements agreeing to protect the security and confidentiality of identifiable information, whenever feasible, identifiers will be removed from study-related information, precautions are in place to ensure the data is secure by using passwords and encryption, because the research involves web-based surveys, audio and/or video recordings of subjects will be transcribed and then destroyed to eliminate audible identification of subjects)

Paper based records will be kept in a secure location and only accessible to individuals directly involved in the study. Electronic information will be stored on restricted access, password protected servers. Subjects are assigned codes once enrolled, but personal

identifiable information will be maintained to be able to access medical records as needed as it pertains to this research. Documentation will contain identifiable information. All electronic information will be maintained behind the UPMC firewall.
